For hemorrhagic stroke or other intracranial bleeding, consultation with a coagulation expert and a neurosurgeon is recommended. See “Major Bleeds” earlier in this section for details relating to how to manage bleeding.

In case of recurrent stroke during the trial, it is at the Investigator's discretion whether study medication will be restarted or whether the patients will be switched to appropriate standard of care antithrombotic treatment.

Reintroduction of study treatment following a stroke (i.e. after recurrent stroke)

The decision about when to restart study medication following a recurrent stroke is at the discretion of the Investigator (with the exception of strokes with mRS of 4 or higher, where restart is not allowed, unless the patient improves to a mRS of 3). [Table 4.1.4: 1](#) shows recommendations ([P12-02400](#)) on the earliest possible time point to start study medication. These recommendations in [Table 4.1.4: 1](#) also apply to restarting study medication after recurrent stroke. Cerebral hemorrhage must be excluded before study drug is restarted. If restarting study medication within 10 days of stroke in patients with mRS of 1, 2 or 3, re-imaging is required to rule out bleeding into the brain (for details see footnote of [Table 4.1.4: 1](#)).

Acute Coronary Syndrome (ACS)

In patients with documented or suspected ACS, study drug should be temporarily discontinued.

Medication Management of ACS

ASA, clopidogrel and glycoprotein IIb/IIIa inhibitors may be administered according to usual clinical practice. However, the concomitant use of these treatments with study medication may increase the risk of bleeding.

For the use of heparins (UFH or LMWH) or other anticoagulants to manage ACS, the following guidance is provided for consideration:

Unfractionated or low-molecular-weight heparin should be withheld until the aPTT is less than 1.5 x ULN (upper limit of normal):

- If the aPTT is between 1.2 and 1.5 x ULN, UF heparin may be commenced preferably without an intravenous loading dose and LMWH may be commenced at the usual therapeutic dose
- If the aPTT is above 1.5 times the ULN, it should be repeated every four hours until it falls below this level, after which heparin or other anticoagulation can be commenced.

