Blinded study medication (either DE or ASA) can be restarted when clinically appropriate (generally ≥ 6 hours after a bolus administration of UFH or ≥ 12 hours after LMWH administration). See [Appendix 10.2.1](#) for recommendations when to start study medication after treatment with parenteral anticoagulants.

Interventional / Surgical Management of ACS or stable CAD

Reperfusion with primary Percutaneous Coronary Intervention (PCI) is preferable over treatment with thrombolysis for patients who are anticoagulated with DE due to the increased

risk for bleeding with concurrent use of thrombolytics and DE. During percutaneous coronary intervention, the activated clotting time (ACT) should be measured and heparin administered as needed according to usual practice.

If primary PCI is not available, the Investigator or treating physician may consider thrombolytic treatment. Thrombolytics should only be administered when the potential gains of reperfusion outweigh the potential risks of severe bleeding. Particular consideration should be given to factors which further increase a patient's risk for bleeding (i.e., elderly, reduced renal function). If the physician elects to treat with thrombolytics, adjunctive treatment with UFH, or LMWH should be withheld until aPTT is ≤ 1.5 times control.

When coronary stent implantation is necessary, bare metal stents (BMS) should be preferred over drug-eluting stents to reduce the time of dual antiplatelet therapy due to stent implantation. Dual antiplatelet therapy will prompt withdrawal of trial-assigned treatment for the duration of dual antiplatelet therapy. The patient may return to study medication at any time once dual antiplatelets are no longer needed. Patients who permanently stop study medication will be followed-up until termination of the trial.

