4.2.2 Restrictions

4.2.2.1 Restrictions regarding concomitant treatment

Corticosteroids, non-steroidal anti-inflammatory drugs (NSAIDs) or anti-rheumatic agents in general should only be used if clinically indicated and benefits are expected to outweigh risks. These medications may increase the risk of gastrointestinal ulcers and gastrointestinal bleeding.

The patients should be advised not to use over-the-counter medications containing additional ASA. In case of the need for pain relief, the use of acetaminophen, diclofenac or ibuprofen instead of ASA should be considered where appropriate. The use of these medications should be limited to the absolute minimum possible time period.

Patients with known need for long-term dual antiplatelet therapy at Visit 1 are excluded from the trial (see [Section 3.3.3](#), exclusion criteria).

The following medications should not be taken concomitantly with study drug:

- ASA (commercial drug /over the counter medications) is not allowed except in the case of CAD where it can be taken if dispensed through IRT as outlined in [Section 4.1.6](#). The use of IRT-assigned ASA should be limited to the absolute minimum possible time period and only if clinically indicated.
- Clopidogrel, ticlopidine, ticagrelor, dipyridamole, dipyridamole+ASA, or prasugrel, and any type of dual antiplatelet therapy
- Vitamin K antagonists (e.g. warfarin, phenprocoumon, acenocoumarol), direct thrombin inhibitors, Factor Xa inhibitors (e.g. rivaroxaban, apixaban, and edoxaban), or other oral anticoagulants
- Fondaparinux, bivalirudin
- Treatment with systemic ketoconazole, itraconazole, posaconazole, cyclosporine, tacrolimus, or dronedarone.
- Concomitant administration of the P-gp inducers rifampicin, St. John`s wort (*Hypericum perforatum*), carbamazepine, or phenytoin, which result in decreased dabigatran plasma concentrations.
- Treatment with parenteral anticoagulants including but not limited to any heparins (UFH or LMWH), and heparinoids (e.g. danaparoid), with the following exceptions:
 - Heparins or other alternate approved parenteral therapy for initial treatment of suspected VTE or ACS if maximum duration is not exceeding 72 hours (see [Section 4.2.1](#)).
- Methotrexate ≥ 15 mg/week

The following medications should not be taken concomitantly with study drug except in clinical scenarios described within [Section 4.2.1](#):

- Fibrinolytic agents (see Section 4.2.1. for exception)

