- GPIIb/IIIa antagonists (e.g. abciximab, tirofiban) (see Section 4.2.1 for exception).

The following medications may potentiate or attenuate the effect of the study medication and may only be used, if expressly instructed by a physician to treat an underlying concomitant disease:

- antidiabetics (e.g. sulphonylurea agents)
- digoxin
- methotrexate < 15 mg/week
- valproic acid

- aldosterone antagonists (spironolactone and canrenoate)
- loop diuretics (e.g. furosemide)
- ACE inhibitors
- uricosuric agents (e.g. probenecid, sulphinpyrazone)
- selective serotonin re-uptake inhibitors (SSRI) or selective serotonin norepinephrine re-uptake inhibitors (SNRIs)

Please see [Appendix 10.2.2](#) for guidance on thrombosis prophylaxis or temporary requirement for a parenteral anticoagulant, which requires a temporary stop of study medication.

Bleeding risk may be increased in patients concomitantly treated with selective serotonin re-uptake inhibitors (SSRI) ([U11-1642-01](#)) or selective serotonin norepinephrine re-uptake inhibitors (SNRIs) ([U12-1072-01](#)).

Co-administration of oral anti-platelet (including ASA) and NSAID therapies increase the risk of bleeding ([U09-3249-02](#)). Specifically, with concomitant intake of antiplatelets or strong P-gp inhibitors in patients aged ≥ 75 years, the risk of major bleeding, including gastrointestinal bleeding, increases.

In patients ≥ 75 years, or with previous gastritis, history of peptic ulcer disease or previous gastrointestinal bleeding, the Investigator should consider prescribing a proton-pump-inhibitor (PPI) based on the local prescribing information while receiving NSAIDs/ASA.

A list of common P-gp inhibitors and P-gp inducers, which may affect plasma concentrations of dabigatran, will be provided in the ISF.

If bleeding is clinically suspected, appropriate measures such as testing for occult blood in stool, or testing for a drop in hemoglobin is suggested ([U12-1072-01](#)). Investigators should assess the benefit-risk of the concomitant use of drugs that can promote bleeding, e.g., NSAIDs, or corticosteroids and use them only when the benefits are thought to outweigh the risks.

Development of an Indication for Anticoagulant Therapy During Follow-Up

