10.2 STUDY DRUG START, THROMBOSIS PROPHYLAXIS AND TRANSITION TO NON-STUDY MEDICATION

10.2.1 When to start study drug following treatment with parenteral anticoagulants, Vitamin K antagonists, or antiplatelets

The following recommendations are provided for guidance only:

Parenteral anticoagulant pre-treatment (e.g. Heparins)

UFH or LMWH/injectable anticoagulant (if given) should be stopped prior to the first dose of study drug. Study drug should be initiated with the following suggested time windows:

- Continuous UFH/other continuous i.v. anticoagulants: initiate study drug at the time the UFH/ other continuous i.v. anticoagulant is stopped
- Bolus of UFH: initiate study drug 6 hours after the bolus injection of UFH
- Low-molecular Weight Heparin/other subcutaneous (s.c.) injectable anticoagulants: initiate study drug 0-2 hours prior to the time that the next dose of the LMWH/other s.c. injectable anticoagulant would be due.

Vitamin K antagonists (VKAs)

- The Vitamin K antagonist should be stopped. Study medication can be given as soon as the INR is < 2.0 .

Antiplatelet pre-treatment

(i.e. ASA, clopidogrel, ticlopidine, prasugrel, ticagrelor, dipyridamole, dipyridamole+ASA, at any labeled maintenance dosage)

- Non-study antiplatelets should be stopped prior to the first dose of study drug. Study drug can be initiated *at any time-point* after discontinuation of the non-study antiplatelet, with one exception: After a loading dose of ticagrelor, clopidogrel or prasugrel has been taken, a minimum of 2 hours should elapse before the first dose of study medication can be given.

Please note that ASA (commercial drug/over the counter medication) ticagrelor, clopidogrel, dipyridamole, dipyridamole+ASA and prasugrel are restricted medications and may not be taken during treatment with study drug. (Note: optional concomitant ASA assigned by IRT may be given, see [Section 4.1.1](#)).

10.2.2 Thrombosis prophylaxis or temporary requirement for parenteral anticoagulant or antiplatelet(s)

Immobilization or intervention may require temporary thrombosis prophylaxis with e.g. UFH or LMWH or antiplatelet(s). Certain interventions may require the use of parenteral anticoagulants.

The following rules should apply, if thrombosis prophylaxis/parenteral anticoagulants are considered temporarily necessary by the Investigator:

[figure not shown]

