- Temporarily stop study medication. It is recommended to wait 12 hours after the last dose of study medication before switching to a parenteral anticoagulant (e.g. UFH, LMWH). Antiplatelet(s) can be started at any time after last dose of study drug.

The period of thrombosis prophylaxis should be kept to a minimum. For recommendations how to switch back to study drug (DE or ASA) see [Section 10.2.1](#).

10.2.3 Transition to non-study antithrombotic treatment with early study drug discontinuation or at the end of the trial

Patients actively taking study drug at their final treatment visit and patients who stop study medication early may need to switch to a non-study antithrombotic treatment at the Investigator's discretion. The following recommendations are provided for guidance only

- If the non-study treatment will be antiplatelet agent(s), this medication can be initiated at any time-point after last intake of study medication.
- If the non-study treatment will be DE or another NOAC (such as rivaroxaban, apixaban or edoxaban), the first dose of DE (or other NOAC) should be taken at the time that the next dose of study medication would have been due.
- If the non-study treatment is a Vitamin K antagonist, the starting time of the VKA should be adjusted according to the patient's CrCl as follows:
 - CrCl \geq 50 mL/min: start VKA 3 days before discontinuing study drug
 - CrCl \geq 30- < 50 mL/min: start VKA 2 days before discontinuing study drug

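### Section 4.2.2.1 excepts heparin for suspected VTE or ACS from its ban on use with study drug, while three other statements call for study drug to be stopped; for suspected VTE no specific text settles which applies

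*Protocol*

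**What the plan says.** Section 4.2.2.1 of the protocol introduces a list with "The following medications should not be taken concomitantly with study drug". One item is "Treatment with parenteral anticoagulants including but not limited to any heparins (UFH or LMWH), and heparinoids (e.g. danaparoid), with the following exceptions". The single exception beneath it is "Heparins or other alternate approved parenteral therapy for initial treatment of suspected VTE or ACS if maximum duration is not exceeding 72 hours", followed by a pointer to Section 4.2.1.

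Three other places deal with the same situation:

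- **Section 4.2.1, Acute Coronary Syndrome:** "In patients with documented or suspected ACS, study drug should be temporarily discontinued". The section then ties the start of heparin to an aPTT below 1.5 x ULN and describes restarting study drug after heparin.
- **Section 4.2.2.1, after the medication lists:** a pointer to Appendix 10.2.2 for a "temporary requirement for a parenteral anticoagulant, which requires a temporary stop of study medication".
- **Appendix 10.2.2:** "Temporarily stop study medication. It is recommended to wait 12 hours after the last dose of study medication before switching to a parenteral anticoagulant".

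For VTE, Section 3.3.4.1 lists its treatment among the reasons for discontinuing study drug, and the last part of Section 4.2.2.1 discontinues study drug once VTE has been identified. Neither addresses the stage at which VTE is only suspected.

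**The concern.** An exception to a ban on concomitant use permits concomitant use. The list's other exception, IRT-dispensed ASA for patients with coronary artery disease, plainly means a drug taken alongside study drug, so the heparin exception is naturally read the same way. Section 4.2 tells investigators that any concomitant therapy is open to them except what Section 4.2.2 excludes, so this is where a site will look.

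Read that way, the exception allows what the other three statements exclude. The consequence differs by arm: under overlap a dabigatran patient receives two anticoagulants, and an ASA patient receives one anticoagulant plus an antiplatelet. The site is blinded and cannot tell which applies. Major bleeding is the primary safety endpoint, and Section 4.1.3 states the aim of superior efficacy without a clinically meaningful excess in bleeding. An unclear instruction about anticoagulant overlap bears directly on that aim.

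**Working it through.** No sample size, power or error rate is involved, and the plan gives no figure to reproduce. The check is a comparison of passages for each clinical situation.

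| Situation | 4.2.2.1 exception | 4.2.1 | Later sentence of 4.2.2.1 | Appendix 10.2.2 |
|---|---|---|---|---|
| Suspected ACS | Heparin with study drug, up to 72 h | Interrupt study drug; aPTT condition; restart later | Stop | Stop; 12 h wait recommended |
| Suspected VTE | Heparin with study drug, up to 72 h | No text | Stop (general) | Stop (general); 12 h wait recommended |
| VTE identified or treated | Not addressed | No text | Study drug discontinued (also 3.3.4.1) | Not needed |

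**Suspected ACS.** The exception and 4.2.1 conflict as written. A site that follows the exception's own cross-reference reaches the instruction to interrupt study drug, so the conflict is likely to be noticed and resolved.

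**Suspected VTE.** The same cross-reference leads to a section that covers procedures, bleeding, stroke, ACS and overdose but not VTE. What remains is a specific permission on one side and two general statements on the other. Of the general statements, one is a clause inside a pointer. The other, in 10.2.2, opens with immobilization and interventions before stating its rules for any parenteral anticoagulant judged temporarily necessary. No aPTT step is given for suspected VTE, and Sections 4.1.5.2 and 4.2.1 discourage coagulation tests outside emergencies and urgent situations.

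**Scale of the permitted overlap.** Inputs: 72 hours (4.2.2.1) and dabigatran twice daily at about 12-hour intervals (4.1.4).

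- Doses within the window under the exception: 72 / 12 = 6, if the full period is used and none is withheld.
- Doses under the stop statements: 0.

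**SAP listing.** In SAP Table 6.2: 1, violation D2 (prohibited medication) is defined by reference to protocol Section 4.2.2.1, which contains both the exception and the contrary sentence. Violation C3.1 covers treatment not interrupted when required, and its example column names AF and CrCl below 30 mL/min. Whether overlap within 72 hours would be listed is therefore undetermined. Both codes exclude patients from no analysis set.

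**The case against.** The strongest reply is that a site overlapping heparin with study drug is following one bullet and not the protocol. The cross-reference takes an ACS case to the stop rule, the same section later says a stop is needed, 10.2.2 agrees, and identified or treated VTE ends study drug. The sponsor may well have meant that heparin is allowed in the trial with study drug paused. This stands in part. It shows that most of the text points one way and that the practical gap is mainly suspected, unconfirmed VTE. It does not remove the conflict, because the exception, under its list header, does not say that study drug is paused.

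A reader might also infer more than the documents support:

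- **That the conflict decides which bleeds are counted as on-treatment.** It does not. The on-treatment period runs to last intake plus 6 days, that is 6 x 24 = 144 hours. A 12-hour wait followed by 72 hours of heparin ends at 84 hours, so bleeds in that span are counted under either reading. Bleeding risk could differ; the counting rule does not.
- **That the SAP would certainly fail to flag overlap.** D2 cites the whole section, including the stop sentence, and the C3.1 entries stand in an example column. This is an ambiguity in a listing.
- **That the restart intervals also contradict each other.** Section 4.2.1 gives "generally ≥ 6 hours after a bolus administration of UFH or ≥ 12 hours after LMWH administration", and Appendix 10.2.1 says to "initiate study drug 0-2 hours prior to the time that the next dose of the LMWH/other s.c. injectable anticoagulant would be due". The LMWH interval is not stated. If it is 12 hours, 10.2.1 gives 10 to 12 hours; if 24 hours, it gives 22 to 24 hours, which meets the 4.2.1 condition. The UFH bolus guidance agrees at 6 hours. Both are soft recommendations, and 4.2.1 refers to 10.2.1. No contradiction is shown.

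**Conclusion.** The point holds as an internal inconsistency in the current protocol. The 4.2.2.1 exception, read under its list header, permits a parenteral anticoagulant together with study drug for up to 72 hours, against Section 4.2.1 for ACS and against 4.2.2.1 itself and Appendix 10.2.2 in general. The exposed case is suspected VTE, for which no specific text resolves the matter.

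The size is limited and partly unknown. The overlap ceiling is 6 scheduled dabigatran doses per episode, assuming 12-hour dosing, full use of the 72 hours and no dose withheld. The documents project no number of suspected VTE or ACS episodes, so no effect on the bleeding comparison can be estimated. Power and the primary analysis on the randomized set are not affected.

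The stop statements differ in force: 4.2.1 and 10.2.2 are worded as advice on what should be done, and the 12-hour wait is a recommendation, while the later sentence of 4.2.2.1 is worded as a requirement. Confidence is high for the textual conflict. This review takes no view on which rule is clinically right.

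**What to change.** Reconcile the exception and the later sentence in Section 4.2.2.1, the ACS text in Section 4.2.1, and Appendix 10.2.2, so that one rule states whether study drug is stopped while a parenteral anticoagulant is given. The rule should name suspected VTE as well as suspected ACS, and the cross-reference should lead to text covering both. The choice of rule belongs to the sponsor.

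Then align SAP Table 6.2: 1 so that D2 and C3.1 state whether overlap of study drug with a parenteral anticoagulant is listed as an important violation under that rule.

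The cost is protocol wording, a letter to sites and an edit to two SAP table entries. No new data and no additional patients are needed.

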4.2.2.2 Restrictions on diet and life style

There are no specific dietary restrictions with DE or with ASA.

4.3 TREATMENT COMPLIANCE

Patients are requested to bring all remaining trial medication including empty package material with them to all visits.

Treatment compliance for capsules (DE or matching placebo) and tablets (ASA and matching placebo) will be checked by the study staff at Visit 3 and all future visits, and will be recorded in the eCRF. The compliance check will be based on the number of capsules/tablets missing (i.e. actually taken) accountability log.

Medication compliance should be $\geq 80\%$ but $\leq 120\%$. If compliance does not meet this range, an explanation for this deviation should be given and recorded in the eCRF. Non-compliant patients should be advised about the importance of taking study medication strictly as directed. If the investigator or staff detect compliance is out of range on two occasions, the Investigator should notify the Sponsor. Withdrawal from treatment may then be considered after discussion and agreement between Investigator and Sponsor.

Decisions about evaluability of patients will be made at the Blinded Report Planning Meeting (BRPM) and at the latest prior to database lock.

5. VARIABLES AND THEIR ASSESSMENT

5.1 EFFICACY

5.1.1 Endpoints of efficacy

The primary endpoint in this trial is time to first recurrent stroke (ischemic, hemorrhagic and unspecified).

The key secondary efficacy endpoints are (both time to event endpoints):

- Ischemic stroke
- Composite endpoint of nonfatal stroke, nonfatal MI and cardiovascular death

For statistical error probability considerations for key secondary endpoints, refer to [Section 7.3.2](#).

Other Secondary efficacy endpoints (all time to event endpoints):

- Disabling stroke (modified Rankin Scale ≥ 4 , as determined 3 months after recurrent stroke)
- All-cause death

5.1.2.2 Systemic embolism

Systemic embolism is an acute vascular occlusion of the extremities or any organ (kidneys, mesenteric arteries, spleen, or grafts) and must be documented by angiography, surgery, scintigraphy or autopsy.

5.1.2.6 Venous Thromboembolism

All VTEs should have objective verification by definitive diagnostic evaluation (e.g. Doppler/compression ultrasound (CUS), venography).

In case of death, autopsy is an additional way to confirm VTE.

Deep Vein Thrombosis

Deep Vein Thrombosis (DVT) is generally documented by one of the following:

- Abnormal CUS
- An intraluminal filling defect on venography
- At autopsy

Pulmonary embolism

Pulmonary embolism is generally documented by one of the following:

- An intraluminal filling defect in segmental or more proximal branches on spiral CT scan
- An intraluminal filling defect or an extension of an existing defect or a sudden cut-off of vessels more than 2.5 mm in diameter on the pulmonary angiogram
- Perfusion defect of at least 75% of a segment with a local normal ventilation result (high-probability) on ventilation/perfusion lung scan (VPLS)
- Inconclusive spiral CT, pulmonary angiography or lung scintigraphy with demonstration of DVT in the lower extremities by CUS or venography
- At autopsy

